12.11.6. Pharmacodynamic Figures

Efficacy: Figures					
No.	Population	IDSL / Example Shell	Title	Programming Notes	Deliverable [Priority]
PainCart					
2.01.	UVB-MITT	PD_F1	Ratio to Baseline in UVB Heat Pain Detection	Programming note: Include footnote on how the ratio to baseline was derived. State original unit of pain assessment.	SAC [1]
2.02.	MITT	PD_F1	Ratio to Baseline in Cold Pressor Time to Intolerable Pain Threshold	Programming note: Include footnote on how the ratio to baseline was derived. State original unit of pain assessment.	SAC [1]
2.03.	MITT	PD_F1	Ratio to Baseline in Electrical Pain Tolerance Threshold – Single Stimulus	Programming note: Include footnote on how the ratio to baseline was derived. State original unit of pain assessment.	SAC [1]

Efficacy: Figures					
No.	Population	IDS / Example Shell	Title	Programming Notes	Deliverable [Priority]
2.04.	UVB-ITT	PD_F1	Individual Ratio to Baseline in UVB Heat Pain Detection	Programming note: Include footnote on how the ratio to baseline was derived. State original unit of pain assessment.	SAC [1]
2.05.	ITT	PD_F1	Individual Ratio to Baseline in Cold Pressor Time to Intolerable Pain Threshold	Programming note: Include footnote on how the ratio to baseline was derived. State original unit of pain assessment.	SAC [1]
2.06.	ITT	PD_F1	Individual Ratio to Baseline in Electrical Pain Tolerance Threshold – Single Stimulus	Programming note: Include footnote on how the ratio to baseline was derived. State original unit of pain assessment.	SAC [1]
Target Engagement Concentrations					
2.07.	Safety	PK16A	Individual Free & Total Serum CCL17 Concentration-Time Plots (Linear and Semi-log)	IDS. By participant, endpoint and treatment sequence Period is presented on the same plot, with linear and semi-logarithmic scale side by side	AAC [1]
2.08.	Safety	PK17	Mean Free & Total Serum CCL17 Concentration-Time Plots (Linear and Semi-log) by Treatment	IDS. By endpoint and treatment sequence. Period is presented on the same plot, with linear and semi-logarithmic scale side by side.	AAC [1]
2.09.	Safety	PK18	Median Free & Total Serum CCL17 Concentration-Time Plots (Linear and Semi-log) by Treatment	IDS. By endpoint and treatment sequence. Period is presented on the same plot, with linear and semi-logarithmic scale side by side.	AAC [1]

12.11.7. Safety Tables

Safety: Tables – All Safety Tables will be presented by Period unless stated otherwise.					
No.	Population	IDS / Example Shell	Title	Programming Notes	Deliverable [Priority]
Adverse Events (AEs)					
3.01.	Safety	AE1xo	Summary of All Adverse Events by System Organ Class and Preferred Term by Period	ICH E3 Present by Period Programming note: For interim analysis present AEs SOCs and PTs which have more than 2 subjects overall per period. i.e. at least two unique subjects in the Total column per period. Include footnote: Note: For interim, only AEs occurring in two or more subjects by period are reported.	IA 1 [1], IA 2 [2], SAC [3]
3.02.	UVB-Safety	AE1xo	Summary of All Adverse Events by System Organ Class and Preferred Term by Period – UVB Participants Only	ICH E3 Present by Period	SAC [1]
3.03.	Safety	AE1xo	Summary of All Adverse Events by System Organ Class and Preferred Term - Overall	ICH E3 Present Placebo, GSK3858279, Total Columns	SAC [1]
3.04.	Safety	AE5A	Summary of All Adverse Events by System Organ Class and Preferred Term and Maximum Intensity by Period	ICH E3	SAC [1]
3.05.	Safety	AE1xo	Summary All Drug-Related Adverse Events by System Organ Class and Preferred Term by Period	ICH E3	SAC [1]
3.06.	Safety	AE5A	Summary of All Drug-Related Adverse Events by System Organ Class and Preferred Term and Maximum Intensity by Period	ICH E3	SAC [1]
3.07.	Safety	AE3	Summary of Non-Serious Drug-Related Adverse Events by Overall Frequency by Period	PLS Requirement	SAC [1]

Safety: Tables – All Safety Tables will be presented by Period unless stated otherwise.					
No.	Population	IDSL / Example Shell	Title	Programming Notes	Deliverable [Priority]
3.08.	Safety	AE15	Summary of Common (>=5%) Non-serious Adverse Events by System Organ Class and Preferred Term (Number of Participant and Occurrences) by Period	FDAAA, EudraCT	SAC [1]
Serious and Other Significant Adverse Events					
3.09.	Safety	AE16	Summary of Serious Adverse Events by System Organ Class and Preferred Term (Number of Participants and Occurrences) by Period	FDAAA, EudraCT Produce if more than 5 SAEs are reported.	SAC [1]
3.10.	Safety	AE3	Summary of Serious Drug-Related Adverse Events by Overall Frequency by Period	PLS Requirement	SAC [1]

Safety: Tables – All Safety Tables will be presented by Period unless stated otherwise.					
No.	Population	IDSL / Example Shell	Title	Programming Notes	Deliverable [Priority]
Laboratory: Chemistry					
3.11.	Safety	LB1	Summary of Chemistry Changes from Baseline by Period	ICH E3 Present by Period	AAC [1]
3.12.	Safety	LB17	Summary of Worst-Case Chemistry Results by PCI Criteria Post-Baseline Relative to Baseline by Period	ICH E3 Present by period	AAC [1]
Laboratory: Haematology					
3.13.	Safety	LB1	Summary of Haematology Changes from Baseline by Period	ICH E3 Present by Period	AAC [1]
3.14.	Safety	LB17	Summary of Worst Case Haematology by PCI Criteria Post-Baseline Relative to Baseline by Period	ICH E3 Present by Period	AAC [1]
Laboratory: Urinalysis					
3.15.	Safety	LB1	Summary of Urine Concentration Changes from Baseline by Period	ICH E3 Present by Period	AAC [1]
3.16.	Safety	UR1	Summary of Worst-Case Urinalysis Results (Discrete or Character Values) Post-Baseline Relative to Baseline by Period	ICH E3 Present by Period	AAC [1]
ECG					
3.17.	Safety	EG1	Summary of ECG Findings by Period	IDSL	AAC [1]
3.18.	Safety	EG10	Summary of Maximum QTc Values Post-Baseline Relative to Baseline by Category by Period	IDSL	AAC [1]

CONFIDENTIAL

209973

Safety: Tables – All Safety Tables will be presented by Period unless stated otherwise.					
No.	Population	IDSL / Example Shell	Title	Programming Notes	Deliverable [Priority]
3.19.	Safety	EG2	Summary of Change from Baseline in ECG Values by Day by Period	IDSL	AAC [1]
3.20.	[Safety]	EG11	Summary of Maximum Increase in QTc Values Post-Baseline Relative to Baseline by Category by Period	IDSL	AAC [1]
Vital Signs					
3.21.	Safety	VS1	Summary of Change from Baseline in Vital Signs by Period	ICH E3	AAC [1]
3.22.	Safety	VS7	Summary of Worst-Case Vital Signs Results by PCI Criteria Post-Baseline Relative to Baseline by Period	IDSL	AAC [1]
Laboratory: Hepatobiliary (Liver)					
3.23.	Safety	LIVER1	Summary of Liver Monitoring/Stopping Event Reporting by Period	IDSL Programming Note: Subjects should be recorded under the treatment they are receiving at the time the liver monitoring/stopping event is reported, or if the liver monitoring/stopping event was reported during a washout period, under the last study treatment received. Only produce if there is a liver event	AAC [1]

CONFIDENTIAL

209973

Safety: Tables – All Safety Tables will be presented by Period unless stated otherwise.					
No.	Population	IDSL / Example Shell	Title	Programming Notes	Deliverable [Priority]
COVID-19					
3.24.	Safety	PAN1A	Summary of COVID-19 Assessments for Subjects with Suspected, Probable or Confirmed COVID-19 Adverse Events by Period	Present by Period. Treatment columns as: Placebo and GSK3858279 COVID-19 recommended display	AAC [1]

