7. DISCONTINUATION OF STUDY INTERVENTION AND PARTICIPANT DISCONTINUATION/WITHDRAWAL

7.1. Study Stopping Criteria

Recruitment will be halted by the sponsor if any of the following occur in participants receiving GSK3858279:

- Two participants experience the same SAE that is considered related to GSK3858279
- Two participants experience the same significant clinical or significant laboratory abnormality that may plausibly relate to GSK3858279 (according to the clinical judgement of the investigator)
- Two participants present with unexplained and clinically significant mucocutaneous bleeding (according to the clinical judgement of the investigator and medical monitor) that is considered causally related to GSK3858279.

Recruitment may be resumed after appropriate positive review of safety findings by the Principal Investigator and GSK Medical Monitor and following approval to restart the study from the regulatory agency and ethics committee.

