9.5. Interim Analyses

Two interim analyses may occur during the conduct of the study:

- An interim analysis may be performed once the final UVB-MITT participant in period 3 has completed the day 15 assessments of the PainCart. At the interim, PainCart, safety, demographics, PK and TE data will be reviewed by the Project Leader and selected members of the Project Team and CPEM Leadership.

Dependent on the results observed in the cold pressor and electrical pain single stimulus tolerance endpoints, the study could be stopped for futility. A secondary objective for the interim may be to use the analysis for internal decision-making purposes. An interim analysis may be performed once the final participant in period 3 has completed the day 15 assessments of the PainCart. The interim analyses will be used for internal decision making only, no changes to the study can occur.

Further details of the interim analyses will be provided in the interim charter. The Reporting and Analysis Plan will provide further information on the planned statistical analyses performed at the interim analyses.

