2.3. Study Design

This study will be a randomized, double-blind, placebo-controlled, three-period two-treatment incomplete-block crossover study in healthy participants to investigate the effects of IV GSK3858279 on evoked pain tests in the PainCart. The study will be performed in a single centre.

In each period participants will receive either GSK3858279 or placebo in a 1:1 ratio. During the trial participants will receive both treatments, participants will receive either two doses of GSK3858279 and one dose of placebo, or two doses of placebo and one dose of GSK3858279 with equal likelihood, the order of treatment assignments will be randomised.

The total duration of the study (from signing informed consent until final follow-up visit) for each participant will be approximately 6 months. Study participation may be prolonged in the event the study is on-hold. Screening period will be a maximum of 28 days prior to study procedures, each study period will be approximately 2 weeks with at least a 4-week wash-out period between dosing (i.e. Day 1) in each of the study periods, final follow-up visit will be at approximately 8 weeks after last dose.

Participants will arrive at the research unit either one or two days before dosing, for the non-UVB-MITT and UVB-MITT group respectively. After arrival, subjects will be tested for SARS-CoV-2. Urine will be screened for the presence of drugs and an alcohol breath test will be performed. For participants with a positive urine drug screen or alcohol breath test, the treatment occasion may be rescheduled at the discretion of the principal investigator and GSK medical monitor. UVB irradiation will be applied approximately 24 hours before dosing in the UVB-MITT population only. ECG and vital signs will also be performed.

Participants will be assigned to receive treatment and pain assessments during either morning or afternoon sessions. They will continue to receive treatment and pain assessments at approximately the same time of day throughout all three study periods.

Meals will be served at the site scheduled times. Safety, PK, PD and PainCart assessments will be performed as outlined in the SoA. Baseline measurements for PainCart (2 baseline measurements) are conducted at each study period prior to dosing.

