3. PLANNED ANALYSES

3.1. Interim Analyses

Two interim analyses of the primary endpoints to inform internal decision making may be conducted during the study. The interim analyses may occur when:

- The final UVB-MITT participant (approx. 15 evaluable participants) to have completed the day 15 assessments of the PainCart assessments in study period 3 (final study period).
- The final randomised participant has completed the day 15 assessments of the PainCart assessments in study period 3 (final study period).

The table below details the endpoints that will be analysed/summarised at the interim:

Purpose of Interim	Endpoints
Interim Analysis 1 (Futility)	
UVB heat pain detection (Celsius)
 
 • Absolute values (Summarised) • Change from baseline (Summarised) • Ratio to Baseline (Summarised) • AAUC of Ratio to Baseline (Analysed) 
Cold pressor time to intolerable pain threshold (seconds):
 
 • Absolute values (Summarised) • Change from baseline (Summarised) • Ratio to Baseline (Summarised) • AAUC of Ratio to Baseline (Analysed) 
Electrical pain tolerance – single stimulus (mA):
 
 • Absolute values (Summarised) • Change from baseline (Summarised) • Ratio to Baseline (Summarised) • AAUC of Ratio to Baseline (Analysed) 
Summary of Demographic Characteristics
 
Summary of Derived Serum GSK3858279 Pharmacokinetic Parameters (non-transformed and log-transformed)
 
Summary of Serum GSK3858279 Concentration-Time Data (ng/mL)
 
Summary of Derived Free and Total CCL17 in Serum Target Engagement Parameters (non-transformed and log-transformed)

	
Summary of Free & Total CCL17 in Serum Concentration-Time Data (pg/mL).
 
Summary of All Adverse Events by System Organ Class and Preferred Term by Period (>=2 Subjects with the AE)

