IA 2 – Internal Decision-Making Purposes	
UVB heat pain detection (Celsius)
 
 • Absolute values (Summarised) • Change from baseline (Summarised) • Ratio to Baseline (Summarised) • AAUC of Ratio to Baseline (Analysed) 
Cold pressor time to intolerable pain threshold (seconds):
 
 • Absolute values (Summarised) • Change from baseline (Summarised) • Ratio to Baseline (Summarised) • AAUC of Ratio to Baseline (Analysed) 
Electrical pain tolerance – single stimulus (mA):
 
 • Absolute values (Summarised) • Change from baseline (Summarised) • Ratio to Baseline (Summarised) • AAUC of Ratio to Baseline (Analysed) 
Summary of Demographic Characteristics
 
Summary of All Adverse Events by System Organ Class and Preferred Term by Period

Note: Ratio to baseline will only be produced if deemed suitable by the distribution of the parameters.

Note: AAUC = Analysis Area Under Curve. Derivation of AAUC is described in Section [12.6.3](#) Pharmacodynamic.

The statistical methods of the analyses are described in Section [7.1](#), Section [7.2](#) and Section [7.3](#).

The following functions will be unblinded to interim analysis data: Clinical Statistics, Clinical Programming and CPMS. Other members of GSK will be unblinded to group level summary data following the interim analyses (as documented in the Interim Charter).

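### The SAP's one listed interim safety table counts adverse events within a single period, so about two-thirds of events seen on drug in exactly two participants would have no preferred-term row unless placebo cases add to the count

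*SAP*

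**What the plan says.** Protocol 9.5 makes safety part of the first interim: "At the interim, PainCart, safety, demographics, PK and TE data will be reviewed". In SAP 3.1 the only safety entry for that interim is "Summary of All Adverse Events by System Organ Class and Preferred Term by Period (>=2 Subjects with the AE"). For the second interim the entry is "Summary of All Adverse Events by System Organ Class and Preferred Term by Period", with no threshold.

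In the SAP display lists (12.11.7 and 12.11.12), Table 3.01 is the only safety output with an interim tag. The overall AE table (3.03), the SAE tables (3.09, 3.10) and the SAE listings (19, 20) are tagged for the final SAC milestone only. Laboratory, ECG, vital-sign and liver displays are tagged for AAC only.

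The programming note to Table 3.01 states the interim cut three times:

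- "For interim analysis present AEs SOCs and PTs which have more than 2 subjects overall per period"
- "at least two unique subjects in the Total column per period"
- in the footnote, "only AEs occurring in two or more subjects by period are reported"

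SAP 2.3 states that "In each period participants will receive either GSK3858279 or placebo in a 1:1 ratio", and SAP 5.1 lists two sequences, A/P/P and P/A/A.

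Protocol 7.1 counts without regard to period. Its first halting criterion, for participants receiving drug, is "Two participants experience the same SAE that is considered related to GSK3858279".

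**The concern.** A minimum-count filter usually serves to keep a table short. Here it is applied separately within each period of a crossover in which the two sequences never receive drug in the same period. Two participants with the same on-drug event, one from each sequence, are two counts of one and produce no row. The same happens to two P/A/A participants if one has the event in Period 2 and the other in Period 3.

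The loss is greatest for terms that are rare on placebo, which are the more informative ones when looking for a drug effect. There is no data monitoring committee (Protocol 1.1), site staff are blinded, and the first interim comes before a possible 12 further participants (SAP 7.1.5.1.2). What that table leaves out therefore matters, chiefly for non-serious events, which have no separate reporting and unblinding route of the kind that exists for SAEs.

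**Working it through.** The documents state no detection probability for this display, so there is no plan figure to reproduce.

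**Inputs**

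- Participants at the first interim: taken as 18, the approximate UVB enrolment (SAP 2.3). This agrees with 18 + 12 = 30.
- Sequences: A/P/P and P/A/A (SAP 5.1), taken as 9 each.
- Drug participant-periods: 9 (A/P/P, Period 1) + 9 (P/A/A, Period 2) + 9 (P/A/A, Period 3) = 27.
- Threshold: two or more participants within a period, all treatments combined.
- Each affected participant has one on-drug event.

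**Exactly two participants, no placebo case**

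- All pairs from different participants: C(27,2) − 9 = 351 − 9 = 342.
- Pairs in the same period, shown: 3 × C(9,2) = 3 × 36 = 108, or 108/342 = 31.6%.
- One from each sequence, never in the same period: 9 × 18 = 162, or 47%.
- Two P/A/A participants in different periods: 9 × 9 − 9 = 72.
- Hidden: (162 + 72)/342 = 234/342 = 68.4%.

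**Sensitivity.** The enumeration was repeated with 18 and 30 participants, two and six sequences, equal risk per dose or per participant, and equal period lengths or assumed lengths of 27:27:56 days. The hidden share runs from 62% to 69%.

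**Placebo cases.** The filter reads the Total column, so one placebo case in either of the two periods restores a row. With 9 placebo participants in each of those periods and a placebo rate p per participant-period, hidden share = 0.684 × (1 − p)^18:

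| p | Hidden |
|---|---|
| 0 | 68% |
| 1% | 57% |
| 2% | 48% |
| 5% | 27% |
| 10% | 10% |

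**More than two participants, no placebo case**

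- Three: all must fall in different periods. With equally likely, independent periods this is 3!/3³ = 6/27 = 22%. An exact count for the two sequences gives 9 × 9 × 8 = 648 of 672 + 1,296 + 648 + 84 = 2,700 triples, or 24%.
- Four or more: with three periods, at least two must share one, so a row always appears.

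**Effect of counting across periods.** The chance that a drug-only term gets a row, treating the 27 doses as independent:

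| Rate per dose | Within a period | Across periods |
|---|---|---|
| 5% | 20% | 39% |
| 10% | 54% | 77% |

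The first column is 1 − [P(at most 1 of 9)]³ and the second is P(at least 2 of 27). The second is slightly generous, because two events in one P/A/A participant would count as one participant.

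**Threshold wording.** Read literally, the first sentence of the note requires three participants in a period and hides 100% of drug-only events in two participants. The other two statements in the note, and the first-interim entry in SAP 3.1, require two. SAP 3.1 sets no threshold for the second interim, whereas the Table 3.01 note filters interim output generally.

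**The case against.** A reader might infer that every isolated SAE is invisible to the sponsor, or that a treatment imbalance can be seen only in this table. The documents do not support either reading. All SAEs go to the sponsor within 24 hours (Protocol 8.2.1), and safety staff may unblind any of them (Protocol 6.3.2). An SAE that shares its preferred term with another participant in the same period does get a row, although nothing marks it as serious. A system-organ-class row can also survive when its preferred term does not. The interim charter, cited in Protocol 9.5 and SAP 3.1, could add displays.

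It would also go too far to say that the stopping rule depends on this filter. Protocol 7.1 does not operate through Table 3.01, and it covers related SAEs, plausibly related significant abnormalities and causally related bleeding, not any shared term. The stopping decision at the first interim rests on the pain endpoints, so this is a futility look with a safety summary attached.

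Two further objections stand. Only sparse events are lost, and two cases against none among 18 participants is weak evidence of imbalance. SAP 1.1 records that the study was terminated for not meeting the futility threshold, so nothing can now be gained at that interim.

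What these points leave untouched is that the listed display drops sparse on-drug events because of how the sequences are laid out, and that its threshold is stated inconsistently.

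**Conclusion.** The point holds in a limited form. Under the two-participant reading, with about 18 participants in balanced sequences and one on-drug event per affected participant, roughly two-thirds of events seen on drug in exactly two participants would have no preferred-term row. That figure requires that no placebo participant has the same term in those periods; at a 5% placebo rate it is about a quarter. The loss is 22% to 24% for three participants and nil for four or more. An SAE whose term occurs in only one participant in that period also has no preferred-term row, though the sponsor learns of it by another route.

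Separately, and without any assumption, the Table 3.01 note contradicts itself on the threshold, and SAP 3.1 and 12.11.7 disagree on whether the second interim is filtered. Because the charter is not available, the conclusion covers the displays that the SAP lists, not everything the interim reviewers may have received.

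**What to change.** 1. State one threshold in the Table 3.01 note, and make SAP 3.1 and 12.11.7 agree on whether it applies to the second interim.
2. Tag the existing Table 3.03 (all periods combined, by treatment) for the interims, or keep Table 3.01 and apply the two-participant count across all periods.
3. Exempt serious events from the filter and show them as group-level counts. Adding participant-level listings is harder to justify, because SAP 3.1 gives sponsor staff outside the unblinded functions group-level summaries only.

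The cost is retagging one existing display and editing the notes. The downside is that a row based on a single event may reveal one participant's assignment to the interim reviewers, who under Protocol 6.3.2 have no direct contact with the site or participants. Since the study has ended, the practical step now is to state, in any account of the interim safety review, which threshold was applied.

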1.3.2. Study periods 1, 2, 3 and Early Withdrawal

When the following assessments are scheduled to be performed at the same time-point, the order will be as follows:

ECG > vital signs > PK and PD sampling > PainCart

Procedure	Study periods 1, 2, 3 (Days)								Early Withdrawal	Notes
	-2	-1	1	2	7	8	15	25		
Out-patient visit					X*	X	X		X	Optional in-clinic stay for participants at the discretion of investigator. *Day 7 is optional for those participants not receiving UVB.
Admission in clinical unit	X**									Optional in-clinic stay for participants at the discretion of investigator ** If subjects are not UVB-MITT participants, optional admission will be on Day-1 with Day-2 assessments completed on Day-1.
Discharge from clinical unit				X						Except if, the participant needs to remain in the Unit longer for medical reasons.
Phone Call							X			AE collection - may be out-patient visit at discretion of Investigator for additional checks
Brief Physical Examination			X	X		X	X		X	
Haematology, clinical chemistry (include liver chemistries) and urinalysis		X	X	X		X	X		X	Troponin T to be assessed on Day -1, 8, 15 (and EW if needed). C3/C4 on Day -1 only
UrDrug, BrAlc		X			X*		X			*for volunteers who do not receive UVB application, the Day 7 Assessments may be performed on Day 8 prior to PainCart
SARS-CoV-2 PCR test or rapid antigen test	X**								X	

Procedure	Study periods 1, 2, 3 (Days)								Early Withdrawal	Notes
	-2	-1	1	2	7	8	15	25		
12-lead ECG		T	X			X	X		X	Day 1: pre-dose (T), 0.5hr, 1hr post start of infusion. On other days a single measure taken prior to 1 st PainCart assessment. T = Triplicate X = Single
Vital signs (including temperature)	X**	X	X	X	X-t	X	X		X	Day 1: pre-dose, 0.5hr, 1hr, 2hr post start of infusion. X-t: temperature assessment on Day 7 for UVB-MITT population only On other days a single measure taken prior to 1 st PainCart assessment.
Randomization			X							Study period 1 only
Drug/placebo IV infusion			X							Continuous infusion over 1 hour

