10.5. Appendix 5: Liver Safety: Required Actions and Follow-up Assessments

Phase 1 Liver chemistry stopping criteria have been designed to assure subject safety and to evaluate liver event aetiology.

Phase 1 liver chemistry stopping criteria and required follow up assessments

Liver Chemistry Stopping Criteria	
ALT-absolute ALT \geq 3xULN If ALT \geq 3xULN AND bilirubin ^{1,2} \geq 2xULN (>35% direct bilirubin) or international normalized ratio (INR) >1.5 , Report as an SAE. See additional Actions and Follow Up Assessments listed below	
Required Actions and Follow up Assessments	
Actions	Follow Up Assessments

 • Immediately discontinue study intervention • Report the event to GSK within 24 hours • Complete the liver event CRF, and complete an SAE data collection tool if the event also meets the criteria for an SAE² • Perform liver event follow up assessments • Monitor the participant until liver chemistries resolve, stabilise, or return to within baseline (see MONITORING below) 
MONITORING:
 
If ALT\geq3xULN AND bilirubin \geq 2xULN or INR >1.5
 
 • Repeat liver chemistries (include ALT, aspartate transaminase [AST], alkaline phosphatase, bilirubin and INR) and perform liver event follow up assessments within 24 hours • Monitor participant twice weekly until liver chemistries resolve, stabilise or return to within baseline • A specialist or hepatology consultation is recommended 	
 • Viral hepatitis serology³ • Obtain INR and recheck with each liver chemistry assessment until the transaminases values show downward trend • Obtain blood sample for pharmacokinetic (PK) analysis as soon as possible, and at least within 7 days, post last dose⁴ • Serum creatine phosphokinase (CPK) and lactate dehydrogenase (LDH). • Fractionate bilirubin, if total bilirubin\geq2xULN • Obtain complete blood count with differential to assess eosinophilia • Record the appearance or worsening of clinical symptoms of liver injury, or hypersensitivity, on the AE report form • Record use of concomitant medications on the concomitant medications report form including acetaminophen, herbal remedies, other over the counter medications. • Record alcohol use on the liver event alcohol intake case report form

Liver Chemistry Stopping Criteria	

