5.2. Baseline Definitions

For all endpoints (except as noted in baseline definitions) the baseline value will be the latest pre-dose assessment with a non-missing value, including those from unscheduled visits. This study has three study periods, with each period having its own baseline which is the latest non-missing value prior to dosing in that period.

For the PainCart test, two assessments are performed at each visit except for visit Day 1 where two are performed prior to dose and two are performed after dose. The baseline value is defined as the mean of the two pre-dose assessments on Day 1 for each study period. If only one pre-dose assessment record is present on Day 1, then this value will be set as the baseline value.

For the PainCart analyses, baseline will compose of two variables:

- Subject level baseline = the mean of the three period baseline values for each subject.
- Period level baseline = Subject level baseline – Period specific baseline value.

Parameter	Study Assessments Considered as Baseline			Baseline Used in Data Display
	Screening	Day -1	Day 1 (Pre-Dose)	
Efficacy				
PainCart Assessments			X	Mean of Day 1 (Pre-Dose) Assessments
Safety				
Vital Signs			X	Day 1 (Pre-Dose)
Haematology			X	Day 1 (Pre-Dose)
Chemistry			X	Day 1 (Pre-Dose)
ECG			X	Day 1(Pre-Dose) [Mean of triplicate measurements]
Urinalysis			X	Day 1 (Pre-Dose)

Unless otherwise stated, if baseline data is missing no derivation will be performed and baseline will be set to missing.

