12.4. Appendix 4: Study Phases and Treatment Emergent Adverse Events

12.4.1. Study Phases

Assessments and events will be classified according to the time of occurrence relative to the start date of the study treatment.

Study Phase	Definition
Pre-Treatment	Date/Time < Study Treatment Dose Date/Time (Period 1)
On-Treatment	Study Treatment Dose Date/Time (Period 1) ≤ Date/Time

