12.4.2. Treatment Emergent Flag for Adverse Events

Flag	Definition
Treatment Emergent	
 • If the AE is on-treatment, then the AE is treatment emergent. • Refer to Section 12.6.1 for period definitions.

NOTES:

- Time of study treatment dosing and start/stop time of AEs should be considered, if collected.

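### Table 3.23 assigns a liver event by when it is reported, not by the qualifying sample, so a pre-infusion value reported after the infusion can be counted under the wrong treatment

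*SAP*

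**What the plan says.** SAP 12.11.7 plans Table 3.23, a by-period summary of liver monitoring and stopping events, produced only if there is a liver event. Its programming note has two clauses. The first is "Subjects should be recorded under the treatment they are receiving at the time the liver monitoring/stopping event is reported". The second continues "or if the liver monitoring/stopping event was reported during a washout period, under the last study treatment received". Neither mentions the time of the sample or of onset.

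Elsewhere the SAP works from occurrence. Section 12.4.1 says "Assessments and events will be classified according to the time of occurrence relative to the start date of the study treatment", and the note to 12.4.2 adds "Time of study treatment dosing and start/stop time of AEs should be considered, if collected".

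The schedule in Protocol 1.3.2 marks the row "Haematology, clinical chemistry (include liver chemistries) and urinalysis" on Days -1, 1, 2, 8 and 15 of each period. SAP 5.2 describes "each period having its own baseline which is the latest non-missing value prior to dosing in that period", and its table takes the chemistry baseline from Day 1 before dosing. Each period therefore has two scheduled samples ahead of its infusion.

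For a participant who meets the liver criterion, Protocol Appendix 5 (10.5) requires the site to "Report the event to GSK within 24 hours" and to "Immediately discontinue study intervention".

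**The concern.** A by-treatment table of liver events should show the treatment that the participant had last been given when the abnormal sample was taken. The note uses a later and partly administrative time. When a sample is drawn just before an infusion and the event is reported just after it, the two times fall on opposite sides of a dose. In this crossover that can mean opposite sides of a change of treatment.

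At stake is one cell of a conditional safety display. The error can run either way: an event that arose after GSK3858279 may appear under placebo, or one that arose on placebo may appear under GSK3858279. Few liver events are to be expected in at most 30 healthy men, so one misplaced event could turn a 1 versus 0 table into 0 versus 1.

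**Working it through.** The plan states no figure to reproduce. The check traces the rule through each sequence and period.

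**Inputs**
- Sequences: A/P/P and P/A/A (SAP 5.1), where A is GSK3858279 and P is placebo.
- One infusion per period, on Day 1, with doses at least 4 weeks apart (Protocol 4.1 and 4.4).
- Pre-infusion chemistry on Day -1 and on Day 1 before dosing (Protocol 1.3.2; SAP 5.2).
- Up to 24 hours to report a liver event (Protocol 10.5).
- Laboratory turnaround: not given. Assumption: the event is reported 0 to 24 hours after the infusion. Only the order matters (sample, infusion, report), so any delay in that range gives the same result.

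**Comparison.** The sample precedes the infusion and the report follows it. After the infusion both clauses give the same answer: the new infusion is the treatment being received, or it is the last one received.

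| Sequence | Period | Last infusion before the sample | Recorded in Table 3.23 | Effect |
|---|---|---|---|---|
| A/P/P | 1 | none | GSK3858279 | pre-treatment value charged to GSK3858279 |
| A/P/P | 2 | GSK3858279 | placebo | opposite arm |
| A/P/P | 3 | placebo | placebo | same arm, later infusion |
| P/A/A | 1 | none | placebo | pre-treatment value charged to placebo |
| P/A/A | 2 | placebo | GSK3858279 | opposite arm |
| P/A/A | 3 | GSK3858279 | GSK3858279 | same arm, later infusion |

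Two sequences with two between-period transitions each give 2 × 2 = 4 transitions. Treatment changes at 2 of them, so 2/4 = 50% would put such an event in the wrong arm, one in each direction. If all six possible orders were used, the count would be 8 of 12 (67%), four in each direction. These are shares of transitions, not probabilities that the case occurs.

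**Can the order arise?** No passage found makes the Period 2 or 3 infusion wait for the Day 1 chemistry result. The recheck in Protocol 1.3.1 concerns randomization or the first dose. The laboratory review in Protocol 8.1.4 has no stated deadline before dosing. For the Day 1 pre-dose sample, the delay need only exceed the gap between sampling and infusion on the same day. For the Day -1 sample it must run past dosing on the following day.

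**The case against.** The strongest reply is that the note already handles most cases. An event reported before the next infusion falls under the washout clause and goes to the treatment last received, which is correct. A stopping result known in time ends dosing under Protocol Appendix 5, so there is no new infusion to be charged. Safety tests are run by the local laboratory (Protocol 10.2), which may return results quickly. The word for reporting may also have been meant loosely, as occurrence. All of this bears on how often the case arises, and it stands. It does not change what the note says when the report comes late.

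Two stronger readings are tempting, and the documents support neither.

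- A reader might take the gap in sampling as the exposed window. At 28-day spacing no chemistry is scheduled from Day 16 to Day 27, which is 12 of 28 days (43%). But a rise that begins then and is still present on Day -1 is caught by the Day -1 sample. If it is reported before dosing, it is assigned correctly. The exposed case is only a qualifying Day -1 or Day 1 pre-dose sample whose report misses the infusion.
- A reader might infer that Table 3.23 plainly contradicts the adverse-event tables. SAP 12.4.1 separates only pre-treatment from on-treatment, relative to the Period 1 dose, and does not assign events to a treatment in Periods 2 and 3. SAP 12.6.1 starts each period on the Day 1 date, so by date alone a Day 1 pre-dose event already lies in the new period, as it would in Table 3.23. The clock-time note in 12.4.2 points the other way, but it applies only if times are collected and does not clearly override the period definition. Disagreement is possible but not established.

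It is also fair to say that an error could be found. Listings 23 and 24 show the laboratory data, Tables 3.11 and 3.12 compare with the pre-dose baseline, and a stopping event has its own case report form.

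**Conclusion.** The rule is wrong as written, and the point is minor. A qualifying pre-infusion sample reported after that period's infusion is recorded under a treatment not yet given when the blood was drawn. That charges a pre-treatment value to treatment in Period 1 and puts the event in the opposite arm in Period 2 of both listed sequences. In Period 3 the arm is right but the infusion is not.

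The conclusion rests on reading the note literally and on a result or report that arrives after the infusion. The second cannot be quantified, because turnaround is not given. The effect is confined to Table 3.23, and no primary result depends on it.

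**What to change.** Replace the programming note with: *Record the event under the last infusion started before the collection date/time of the first sample that met the liver criterion; if that sample preceded the first infusion, record it as pre-treatment.*

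A comparison by date alone is not enough, because under SAP 12.6.1 a Day 1 pre-dose sample already belongs to the new period. Apply the same date/time comparison when assigning adverse events to period and treatment, in line with the note in 12.4.2, so that Table 3.23 and the adverse-event tables agree.

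The cost is one line for Table 3.23 and a clarifying sentence for adverse events. Infusion start is already recorded (SAP 12.6.2). The sample needs a collection time or, on Day 1, at least the pre-dose label that the SAP's baseline rule already relies on. Nothing about dosing or clinical management changes.
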